### 3.5 Endpoints

#### 3.5.1 Primary Endpoints

##### 3.5.1.1 Efficacy - Stage 1

Efficacy will be assessed by the change in TB bacterial load in sputum as a measure of EBA. Bacterial load in sputum at each collection time point will be measured by CFU counts on agar media culture. The EBA will be measured as the slope of the change in log-CFU from baseline (ie, the mean of the values from Day -2 and Day -1) to Day 14.

Protocol 323-201-00003

### 3.5.1.2 Pharmacokinetics - Stage 1

The following PK parameters will be determined for plasma OPC-167832:

- Day 1:  $C_{\max}$ , time to  $C_{\max}$  ( $t_{\max}$ ), and AUC from time zero to time t (the last observable concentration) ( $AUC_t$ ).
- Day 14:  $C_{\max}$  during the dosing interval at steady-state ( $C_{\max,ss}$ ),  $t_{\max}$ ,  $t_{1/2,z}$ , apparent clearance of drug from plasma at steady-state ( $CL_{ss}/F$ ),  $AUC_t$ , AUC calculated over the dosing interval at steady-state ( $AUC_{\tau}$ ), accumulation ratio of  $C_{\max}$  ( $R_{C_{\max}}$ ), and accumulation ratio of AUC ( $R_{AUC}$ ),  $C_{\max}$  normalized to dose ( $C_{\max}/Dose$ ), and  $AUC_{\tau}$  normalized to dose ( $AUC_{\tau}/Dose$ ).

### 3.5.1.3 Pharmacokinetics - Stage 2

The following PK parameters will be determined for plasma OPC-167832, delamanid, and BDQ:

- Day 1:  $C_{\max}$ ,  $t_{\max}$ , and  $AUC_t$ .
- Day 14:  $C_{\max,ss}$ ,  $t_{\max}$ ,  $t_{1/2,z}$ ,  $CL_{ss}/F$ ,  $AUC_{\tau}$ ,  $R_{C_{\max}}$ ,  $R_{AUC}$ , and  $C_{\max}$  normalized to dose ( $C_{\max}/Dose$ ), and  $AUC_{\tau}$  normalized to dose ( $AUC_{\tau}/Dose$ ).

### 3.5.1.4 Pharmacokinetics/Pharmacodynamics - Stage 1

The maximum effect ( $E_{\max}$ ) and exposure producing 80% of  $E_{\max}$  ( $EC_{80}$ ) for OPC-167832, regardless of dose level, will be determined from an exposure-response analysis of the decline of log-CFU count on agar media.

### 3.5.1.5 Pharmacokinetics/Pharmacodynamics - Stage 2

The  $E_{\max}$  and  $EC_{80}$  for OPC-167832 in combination with delamanid and/or BDQ will be determined from an exposure-response analysis of the decline of log-CFU counts on agar media.

### 3.5.1.6 Safety and Tolerability - Stage 1 and Stage 2

Safety and tolerability will be assessed based on the incidence of AEs and the incidence of abnormal findings in clinical laboratory tests (serum chemistry, hematology, urinalysis, and coagulation), physical examinations, vital signs, and electrocardiograms (ECGs).

Protocol 323-201-00003

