#### **7.4.1 Primary Efficacy Endpoint Analyses**

##### **7.4.1.1 Stage 1**

The EBA of OPC-167832 will be determined by the decline in bacterial load.

Individual subject EBA estimates will be obtained using both a two-point EBA calculation as well as a linear-regression based approach. Early bactericidal activity estimates will be derived over the first 14 days (see equation 1 in [Section 7.4.1.1.1](#)).

The EBA for the RHEZ comparator arm will be based on the results for all of the subjects receiving RHEZ treatment in each of the treatment cohorts in stage 1. After the completion of stage 2, the EBA for the RHEZ comparator arm will be recalculated including subjects assigned to the RHEZ regimen in both stage 1 and stage 2.

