# 3 Trial Design

# 3.1 Type/Design of Trial

## 3.1.1 Stage 1

Stage 1 will be a randomized, open-label, active controlled, multiple ascending dose stage in approximately 72 subjects. Dosing is planned to be conducted in 4 sequential cohorts of 18 subjects each:

- Cohort 1: 10 mg OPC-167832 or RHEZ (14 OPC-167832 subjects and 4 RHEZ subjects)
- Cohort 2: 30 mg OPC-167832 or RHEZ (14 OPC-167832 subjects and 4 RHEZ subjects)
- Cohort 3: 90 mg OPC-167832 or RHEZ (14 OPC-167832 subjects and 4 RHEZ subjects)
- Cohort 4: 3 mg OPC-167832 or RHEZ (14 OPC-167832 subjects and 4 RHEZ subjects)

Subjects who signed the informed consent form (ICF) will be admitted to the trial site at screening. Subjects will be screened for up to 4 days (Days -6 to -3) prior to the start of the Day -2 assessments. Screening can be extended up to 7 days. Subjects randomized to OPC-167832 will receive once daily (QD) oral doses of investigational medicinal product (IMP; OPC 167832) from Day 1 through Day 14. After Day 14, the subjects will receive treatment for pulmonary TB according to the local standard of care regimen (RHEZ). In subjects with no clinical indication to start RHEZ immediately, commencement of RHEZ can be delayed for up to 3 days (Days 15, 16, and 17) under close supervision in the trial site hospital ward.

Subjects randomized to RHEZ will receive QD oral doses of RHEZ from Day 1 through Day 20.

Subjects will be discharged on Day 20 once all safety assessments have been completed and all PK samples have been collected.

The safety, tolerability, PK, and efficacy (results from Otsuka TB LAM enzyme-linked immunosorbent assay [ELISA] only) data from each cohort will be reviewed by the trial review team at the end of each cohort. Once all the data for dose selection for the next cohort is available, the data collected from each cohort will be provided to the trial review team. The data will be evaluated to determine if (i) the dose level for the next cohort will be escalated, (ii) the dose level from the previous cohort will be repeated, or (iii) the dose level will be decreased. The dose of OPC-167832 will not exceed the highest tolerated dose studied in the single ascending dose trial, i.e., 480 mg.

Decisions to proceed to the next dose level should be based on, but not limited to, the following safety aspects:

- No death assessed as related to OPC 167832

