# 6 Primary and Secondary Outcome Variables

# 6.1 Primary Outcome Variables

# 6.1.1 Efficacy - Stage 1

Efficacy will be assessed by the change in *Mycobacterium tuberculosis* bacterial (MTB) load in sputum as a measure of EBA. Bacterial load in sputum at each collection time point will be measured by colony-forming unit (CFU) counts on agar media culture. The

EBA will be measured as the slope of the change in log10CFU/mL on agar media from baseline (baseline is defined as the log10 of the mean of Day -2 and Day -1) to Day 14.

### 6.1.2 Pharmacokinetics - Stage 1

The following PK parameters will be determined for plasma OPC-167832:

- Day 1: Maximum (peak) plasma concentration (Cmax), time to Cmax (tmax), and area under the concentration-time curve (AUC) from time zero to time t (the last observable concentration) (AUCt).
- Day 14: Cmax during the dosing interval at steady-state (Cmax,ss), tmax, terminal-phase elimination half-life (t1/2,z), apparent clearance of drug from plasma at steady-state (CLss/F), AUCt, AUC calculated over the dosing interval at steady-state (AUCτ), accumulation ratio of Cmax (RCmax), and accumulation ratio of AUC (RAUC), Cmax normalized to dose (Cmax/Dose), and AUCτ normalized to dose (AUCτ/Dose).

### 6.1.3 Pharmacokinetics - Stage 2

The following PK parameters will be determined for plasma OPC-167832, delamanid and BDQ:

- Day 1: Cmax, tmax, and AUCt.
- Day 14:  $C_{max,ss}$ ,  $t_{max}$ ,  $t_{1/2,z}$ ,  $CL_{ss}/F$ ,  $AUC_{\tau}$ ,  $R_{Cmax}$ ,  $R_{AUC}$ , and  $C_{max}$  normalized to dose ( $C_{max}/Dose$ ), and  $AUC_{\tau}$  normalized to dose ( $AUC_{\tau}/Dose$ ).

# 6.1.4 Pharmacokinetics/Pharmacodynamics - Stage 1

The maximum effect ( $E_{max}$ ) and exposure producing 80% of  $E_{max}$  ( $EC_{80}$ ) for OPC-167832, regardless of dose level, will be determined from an exposure-response analysis of the decline of  $log_{10}CFU/mL$  counts on agar media. The results can be found in a separate population PK/PD analysis report.

#### 6.1.5 Pharmacokinetics/Pharmacodynamics - Stage 2

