The study day of baseline is set to be 0 no matter whether the baseline comes from Day - 2 or Day -1 or the average. The derived analysis CFU is log10 transformed in the calculations of decline in bacteria load. The early bactericidal activity (*EBA*) is determined by the rate of decline in log10CFU/mL during the first 14 days of treatment. The rate of decline will be estimated using both a two-point calculation (day 14 and day 0 (baseline)) as well as a linear-regression based approach as discussed in Section 8.1.1.1.1 and Section 8.1.1.1.2.

and

Version Date: 16 May 2022

Protocol 323-201-00003

The effect size for EBA for IMP-1 group relative to that of IMP-2 group is expressed as the ratio of EBA as shown in formula (1). Either Fieller's method or Delta method as described in Sections 8.1.1.2  will be used in the estimation of the confidence interval of the ratio

$$\frac{EBA_{0-14,IMP1}}{EBA_{0-14,IMP2}}\tag{1}$$

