# 8.1.1.1.2 14-Day EBA Estimate Through Linear Mixed Effects Modeling

Another way to estimate the 14-Day EBA is through a linear mixed effect model, using log10CFU/mL as outcome variable, treatment group,

intercept and slope for day includes a random component for each subject.

The model can be specified in formula as follows:

Statistical Analysis Plan

The model can be fit using SAS PROC MIXED procedure.

The estimated EBA is obtained by taking the negative sign of the slopes for each treatment group. Either the Fieller's method or Taylor's method described in Sections 8.1.1.2 will be used in estimating 95% CI for the EBA ratios between treatment groups. The parameters needed as input for the two algorithms include negative slope and the variance covariance matrix for the slopes, represented using symbols  $\hat{\theta}_1$ ,  $\hat{\theta}_2$   $\hat{\sigma}_{11}$ ,  $\hat{\sigma}_{22}$ .

Similar analyses will be performed for log10LAM pg/mL and TTD endpoints (in greater detail in Section 8.2) except that, in estimating the EBA for TTD, a negative sign is not applied to the slope for TTD. For Stage 2, the same model is used, with the groups for Stage 2 being Stage 1 + Stage 2 RHEZ, OPC + DLM, OPC + BDQ, OPC + DLM + BDQ.

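### The SAP leaves the 95% CI for the EBA ratio as Fieller or Delta, with no visible rule and no lead estimate; at these group sizes the Delta interval sits too low

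*SAP*

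**What the plan says.** Protocol 7.4.1.1.1 expresses the Stage 1 effect size as the EBA of OPC-167832 divided by the EBA of RHEZ. Protocol 7.4.1.1.2 leaves the mixed-model details to the SAP, to be settled before database lock.

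**Interval method.** SAP 8.1.1 offers "Either Fieller's method or Delta method" for the ratio. SAP 8.1.1.1.2 says of the mixed model: "Either the Fieller's method or Taylor's method described in Sections 8.1.1.2 will be used". SAP 8.1.1.2 names both methods once more. No visible sentence says which is used, or when. Some text in 8.1.1.1.2 and 8.1.1.2 is redacted.

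**Estimators.** Both are to be run. SAP 8.1.1 states: "The rate of decline will be estimated using both a two-point calculation", together with a regression approach. Neither is called the lead.

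**Endpoint.** Protocol 3.5.1.1 says "The EBA will be measured as the slope of the change in log-CFU from baseline" to Day 14, and SAP 6.1.1 defines it the same way.

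**Group sizes.** Each Stage 1 cohort has 14 OPC-167832 and 4 RHEZ subjects. RHEZ is pooled over cohorts (Protocol 7.4.1.1: "The EBA for the RHEZ comparator arm will be based on the results for all of the subjects receiving RHEZ treatment"), so the denominator has 4 x 4 = 16 subjects.

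**The concern.** A ratio with an estimated denominator has a skewed sampling distribution. Fieller's method respects that skew. The Delta interval is symmetric about the observed ratio and ignores it. With 16 subjects in the denominator the two need not agree, so leaving the choice open leaves the reported limits open.

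Timing adds to this. The trial is open-label, although the microbiology laboratory is blinded (Protocol 3.6). The SAP version dated 16 May 2022 says the Stage 2 dose has already been determined from Stage 1 data that include efficacy (SAP 3.1.2). The interval method is thus still open after some Stage 1 efficacy results are known. Because no formal test is planned, the interval is the main statement of uncertainty about the ratio.

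The two estimators also use different data. The two-point value needs a Day 14 result, and a visit with both cultures contaminated is missing (SAP 8.1.1). The mixed model can still use that subject's other visits. Without a named lead, the reader cannot tell which ratio is the main result.

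**Working it through.** **The plan's own figure.** Protocol 7.4.1.1.1 gives 0.84 log-CFU for delamanid 200 mg and 1.44 for RHEZ over 14 days: 0.84/1.44 = 0.583, the stated 58%. This reproduces.

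**Inputs.** n1 = 14 and n2 = 16 (above); 95% two-sided (SAP 8.1.1.1.2). Assumptions, because the documents do not give them: equal SD in both groups; independent groups, so zero covariance (two-point setting); t on 14 + 16 - 2 = 28 df, t = 2.048; no missing Day 14 values.

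**Formulas**, with r = th1/th2, s11 = SD²/14, s22 = SD²/16:
- Delta: r ± t·r·sqrt(s11/th1² + s22/th2²).
- Fieller: g = t²·s22/th2²; limits [r ± (t/th2)·sqrt(s11 + r²·s22 - g·s11)]/(1 - g). The interval is unbounded if g ≥ 1.

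**One case in full: th1 = 0.84, th2 = 1.44, SD = 0.9.** s11 = 0.81/14 = 0.0579 and s22 = 0.81/16 = 0.0506.
- Delta: sqrt(0.0820 + 0.0244) = 0.326; half-width 2.048 x 0.583 x 0.326 = 0.390; interval 0.194-0.973.
- Fieller: g = 0.102; root = sqrt(0.0579 + 0.0172 - 0.0059) = 0.263; half-width before scaling (2.048/1.44) x 0.263 = 0.374; interval (0.583 ± 0.374)/0.898 = 0.233-1.067.

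| Assumed SD (log10 CFU over 14 days) | Delta | Fieller | Is 1 excluded? |
|---|---|---|---|
| 0.5 | 0.367-0.800 | 0.382-0.823 | both yes |
| 0.7 | 0.280-0.887 | 0.306-0.937 | both yes |
| 0.9 | 0.194-0.973 | 0.233-1.067 | Delta only |
| 1.0 | 0.150-1.016 | 0.197-1.139 | neither |

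**Where they disagree about 1.** Fieller excludes 1 when |th1 - th2| > t·sqrt(s11 + s22); Delta when |th1 - th2| > t·sqrt(s11 + r²·s22). At r = 0.583 the difference is 0.60.
- Fieller needs SD < 0.60/(2.048 x sqrt(1/14 + 1/16)) = 0.80.
- Delta needs SD < 0.60/(2.048 x sqrt(1/14 + 0.340/16)) = 0.96.

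They therefore disagree only for SD between about 0.80 and 0.96. At an observed ratio of 0.7 the band is 0.58-0.66, and at 0.8 it is 0.38-0.42. Above 1 the direction reverses: at 1.25, Fieller alone excludes 1 for SD 0.43-0.48.

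**Repeated-sampling behaviour.** 200,000 simulated trials per setting, SD 30-80% of the RHEZ mean (0.43-1.15 if that mean is 1.44), true ratios 0.6-1.3:

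| | Delta | Fieller |
|---|---|---|
| Truth above the interval | about 3.4-5.2% | about 2.5% |
| Truth below the interval | 0.1-1.7% | about 2.5% |
| Two-sided coverage | about 95% | about 95% |

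The methods disagree on whether 1 is excluded in about 2-16% of trials. Median Fieller width is roughly 2-15% greater. Fieller was unbounded in at most 0.3% of trials.

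**Estimator and interval together.** At a true ratio of 0.583, the four combinations did not all agree on whether 1 is excluded in about 23-30% of 20,000 trials per setting. This assumes a between-subject slope SD of 0.03-0.05 per day and a residual SD of 0.4-0.6, with the mean of per-subject least-squares slopes standing in for the mixed model.

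**The case against.** The strongest reply is that little depends on this interval. Both documents say the trial is not powered for formal tests or comparisons, and neither sets a decision on whether the ratio excludes 1. Cohort dose selection rests on safety, PK and LAM results. That stands, and it rules out several stronger readings that a reader might infer.

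- *One of four primary results may be picked.* Not supported. Protocol 7.4.1.1 and SAP 8.1.1 require both estimators, so both ratios must be produced. What is open is the interval method and which ratio leads.
- *The choice decides whether parity with RHEZ is excluded.* Only conditionally. At an observed ratio of 0.583 it does so only for SD 0.80-0.96, the documents give no SD, and in most simulated trials the methods agree. Parity is also not a criterion of the plan.
- *Delta rejects parity too often.* Not as an error rate. At a true ratio of 1 it excludes 1 in 4.8-5.1% of trials, against 5.0% for Fieller. Two-sided coverage is nominal (94.7-95.4%); only the split between the tails is wrong.
- *The plan has no selection rule.* This cannot be asserted. A rule could sit in the redacted text of 8.1.1.1.2, 8.1.1.2 or the technical appendix. The visible sentences, however, leave the choice open each time.

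It is also fair that the protocol introduces the ratio under the two-point calculation and adds the mixed model afterwards, so the choice of lead belongs to the sponsor. The slope definition of the endpoint still favours the mixed model.

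**Conclusion.** The concern holds as a matter of estimation and pre-specification. As far as the visible text shows, the interval method is unsettled and no lead estimate is named. The two methods are not interchangeable at 14 against 16: Delta limits sit too low, with misses of about 3.4-5.2% above and 0.1-1.7% below where 2.5% each is intended. Fieller's method corrects this at small cost.

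The sizes rest on assumed SDs, equal variances, normal arm means, zero covariance and 28 df. The interval simulation is a two-point setting; the mixed-model Fieller interval was not simulated. The effect is on the reported limits and on the room for selective reporting. It does not invalidate a planned test, because there is none.

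**What to change.** Before database lock, in SAP 8.1.1, 8.1.1.1.2 and 8.1.1.2:

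1. Replace the either-or wording with Fieller's method for every EBA-ratio interval. Use the model's slope variances and covariance for the mixed model, and zero covariance for the two-point estimate.
2. If Fieller gives no finite limits, report the interval as unbounded. Do not switch to Delta: that would apply it where the denominator is least reliable and bring back a data-dependent choice.
3. Name the mixed-model slope ratio as the lead estimate, in line with the slope endpoint, and the two-point ratio as supportive.
4. Use the same interval method for the Stage 2 ratios that SAP 8.2 analyses by the 8.1.1 methods.

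If a redacted passage already holds a selection rule, align the visible sentences with it and check it against items 1-3.

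The cost is a short SAP edit, and intervals that are asymmetric and roughly 2-15% wider in median width under the assumptions above.

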# 8.1.1.1 Estimation of Day 14 Early Bactericidal Activity (EBA)

# 8.1.1.1.1 Two-time Point Early Bactericidal Activity Calculation

The change from baseline in log10CFU/mL count will be summarized using descriptive statistics (mean, standard error, median, min, max) at each visit by treatment group. The change from baseline in log10CFU/mL is calculated as the value post-baseline minus the value from baseline. Endpoints log10LAM pg/mL and MGIT TTD will also be analyzed in the same way.

A simple two-point EBA estimate is obtained by taking a negative sign for the change from baseline in log10CFU/mL at visit Day 14 divided by the number of days since first IMP ((Baseline log10CFU/mL – Postbaseline log10CFU/mL)/(Days since first IMP at Visit Day 14)). A positive value of 14-Day EBA indicates reduction in bacteria load. The study is an inpatient study, and the nominal visit equals to the analysis visit day.

The mean and standard error for 14-Day EBA for each treatment group can be obtained from SAS PROC MEAN procedure, and will be used in the formulas in Sections 8.1.1.2 to calculate the confidence intervals of the ratio between treatment groups.

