- No more than 2 subjects with Grade 4/5 AEs ("Division of AIDS [DAIDS] Table for Grading the Severity of Adult and Pediatric AEs") assessed as related to OPC 167832.

# 3.1.2 Stage 2

The dose of OPC-167832 for Stage 2 has been determined based on the safety, tolerability, PK and efficacy data from Stage 1 of this trial. Based on the Stage 1 PK/PD analysis of OPC-167832 plasma concentrations and reduction in log10CFU/mL, a dose lower than the current 30 mg specified in the protocol may be considered, provided it can offer similar potential for efficacy as the 30 mg dose.

Stage 2 will be a randomized, open-label, active-controlled, parallel group comparison stage comprising of 46 subjects (subjects who were randomized in stage 1 cannot enroll in stage 2).

Subjects who signed ICF will be admitted to the trial site at screening. Subjects will be screened for 4-7 days prior to the start of Day -2 assessments. Eligible subjects will be housed at the trial site until discharge or early termination. All subjects enrolled during this stage of the trial will be randomized prior to first dosing on Day 1 to one of the following 4 treatments in a ratio of 14:14:14:4:

- 30 mg OPC-167832 and 300 mg delamanid QD (14 subjects)
- 30 mg OPC-167832 and 400 mg BDQ QD (14 subjects)
- 30 mg OPC-167832 and 300 mg delamanid and 400 mg BDQ QD (14 subjects)

• RHEZ QD (4 subjects)

Subjects receiving BDQ will take a loading dose of 700 mg BDQ on Day 1 and 500 mg on Day 2. The dose of BDQ will be 400 mg QD for days 3 to 14.

Subjects will be centrally randomized through an interactive voice response system with no stratification.

Subjects randomized to OPC-167832 and/or delamanid and/or BDQ will receive QD oral doses of IMP (OPC-167832 and/or delamanid and/or BDQ) from Day 1 through Day 14. After Day 14, the subjects will receive treatment for pulmonary TB according to the local standard of care regimen (RHEZ). In subjects with no clinical indication to start RHEZ immediately, commencement of RHEZ can be delayed for up to 3 days (Days 15, 16, and 17) under close supervision in the trial site hospital ward.

Subjects randomized to RHEZ will receive QD oral doses of RHEZ from Day 1 through Day 20.

Subjects will be discharged on Day 20 once all safety assessments have been completed and all PK samples have been collected.

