# 4 Sample Size

The trial is not powered for formal statistical hypothesis testing or comparisons. The sample size is based on sample sizes from several similar trials in the literature. It is planned to enroll 72 (18 in each cohort) subjects in stage 1 in 14:4 ratio. Stage 2 will enroll 46 patients in 14:14:14:4 ratio.

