# 7.2 Demographic and Baseline Characteristics

Summary statistics (mean, standard deviation, median, minimum and maximum) will be presented for continuous baseline characteristics. Frequency and percentage of discrete baseline variables will also be presented. Summaries will be presented by treatment groups based on the Randomized Analysis Set.

Demographic and baseline characteristics variables include:

- Age
- Sex
- Race
- Ethnicity
- Weight, Height, BMI
- Baseline CFU/mL count (Actual X1000)
- Baseline CFU/mL count (log10)

- Baseline x-ray
- Baseline HIV Screen
- Baseline FSH
- Baseline Urine/Blood alcohol
- Baseline Urine test for isoniazid (only applicable to protocol dated 26 Feb 2018)

The baselines for lab tests, ECG, vital sign and overnight sputum culture results are summarized with post-baseline results and will be described in later sections.

The analysis will be presented by treatment groups for Stage 1, and Stage 2 with a combined RHEZ group from Stage 1 and Stage 2.

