### 8.1.1.2.2 Estimate EBA Ratio with Taylor's (Delta) method

Formula (2) can be used to estimate the  $100(1-\alpha/2)$  CI for the EBA ratio (IMP-1 divided by IMP-2). For two-point estimate from Section 8.1.1.1.1, the parameter estimates  $\hat{\theta}_1$ ,  $\hat{\theta}_2$ ,  $\hat{\sigma}_{11}$ ,  $\hat{\sigma}_{22}$  come from summary statistics (mean and square of the standard errors), and covariance between EBA for two treatment groups  $\hat{\sigma}_{12}$ The  $\hat{\theta}_1$ ,  $\hat{\theta}_2$ ,  $\hat{\sigma}_{11}$ ,  $\hat{\sigma}_{22}$ ,  $\hat{\sigma}_{12}$  can be estimated using the same method from Section 8.1.1.2.1.

[figure not shown]
$$\frac{\hat{\theta}_1}{\hat{\theta}_2} \pm t_q \frac{\hat{\theta}_1}{\hat{\theta}_2} \sqrt{\frac{\hat{\sigma}_{11}}{\hat{\theta}_1}^2 + \frac{\hat{\sigma}_{22}}{\hat{\theta}_2}^2 - \frac{2\hat{\sigma}_{12}}{\hat{\theta}_1\hat{\theta}_2}} \tag{2}$$

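### The two-point EBA ratio uses raw arm means of change from baseline, with no adjustment of that change for baseline log10 CFU/mL

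*SAP*

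**What the plan says.** The Stage 1 primary efficacy endpoint is the fall in log10 CFU/mL from baseline to Day 14. SAP 8.1.1 plans two estimates of it.

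- **Two-point estimate (SAP 8.1.1.1.1; the same equation is in Protocol 7.4.1.1.1).** "A simple two-point EBA estimate is obtained by taking a negative sign for the change from baseline in log"10 CFU/mL at Day 14 and dividing by days. Then: "The mean and standard error for 14-Day EBA for each treatment group can be obtained from SAS PROC MEAN procedure". SAP 8.1.1.2.2 confirms that the inputs to the ratio interval "come from summary statistics (mean and square of the standard errors"). No covariate is named for this method.
- **Mixed model (SAP 8.1.1.1.2).** A linear model over all visits in which the "intercept and slope for day includes a random component for each subject". Fieller's or the delta method "will be used in estimating 95% CI for the EBA ratios between treatment groups". Part of the fixed-effect list and the formula are missing from the public copy.

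On sample size: "It is planned to enroll 72 (18 in each cohort) subjects in stage 1 in 14:4 ratio". Stage 2 is 14:14:14:4. RHEZ is pooled over the four Stage 1 cohorts and later over both stages (Protocol 7.4.1.1). On allocation in Stage 2: "Subjects will be centrally randomized through an interactive voice response system with no stratification"; Protocol 3.1.1 says the same for Stage 1. SAP 8.2 applies the CFU methods to LAM and TTD. SAP 7.2 tabulates baseline CFU by arm.

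**The concern.** Subtracting baseline removes its influence completely only if Day 14 log10 CFU rises one-for-one with baseline. If the slope is below 1, for instance because a single baseline reading is noisy, subjects who start high tend to record larger falls. An arm that happens to start higher then looks more bactericidal, and the ratio moves with it.

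Three features make baseline differences plausible here:

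- The arms are small and allocation is unstratified.
- Pooled RHEZ subjects come partly from other cohorts or the other stage, and Stage 2 arms are compared with Stage 1 30 mg alone. Those contrasts are not protected by concurrent randomisation. HIV eligibility also differs between stages (Protocol 3.4.3, criterion 12).
- SAP 8.1.1 sets culture-negative visits to 5 CFU/mL, which is 0.70 on the log10 scale. For a subject at that value the recorded fall is baseline minus 0.70, so a higher start gives a larger EBA. LAM has a similar floor at 15 pg/mL, and TTD a cap at 42 days.

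The ratio to RHEZ is the planned effect size, so both its value and the width of its interval matter.

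**Working it through.** **The plan's own figures.** Protocol 7.4.1.1.1 gives 14-day falls of 0.84 (delamanid 200 mg) and 1.44 (RHEZ). 0.84/1.44 = 0.583, which matches the stated 58%. RHEZ numbers: 4 × 4 = 16 in Stage 1, and 16 + 4 = 20 pooled.

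**Assumed inputs.** The documents give no SD and no baseline-to-Day-14 correlation. Write s0 and s14 for the two SDs, r for the correlation, and b = r × s14/s0 for the slope of Day 14 on baseline.

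**1. Precision.** Variance of the change score: s0² + s14² − 2·r·s0·s14. Variance after adjustment: s14²(1 − r²). With equal SDs their ratio is (1 + r)/2. For 14 vs 16 (N = 30), the width ratio also carries the finite-sample factor √(1 + 1/26) = 1.019 and t on 27 rather than 28 df (2.052/2.048).

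At equal SDs and r = 0.5: √0.75 × 1.019 × 2.052/2.048 = 0.88.

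Adjusted width as a fraction of unadjusted width, for the EBA difference:

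| s14/s0 | r = 0.3 | r = 0.5 | r = 0.7 |
|---|---|---|---|
| 1 | 0.82 | 0.88 | 0.94 |
| 1.5 | 0.95 | 1.00 | 1.02 |
| 2 | 1.00 | 1.02 | 0.98 |

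The saving disappears where b is near 1 (for example s14/s0 = 2, r = 0.5, so b = 1). With equal SDs and r = 0.9 it is negligible (0.995). It is larger if Day 14 is the less variable: s0 = 1.0, s14 = 0.9, r = 0.3 gives a large-sample variance ratio of 0.737/1.27 = 0.58.

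**2. Example ratio.** Take an SD of 14-day change of 0.8 log10, equal SDs, r = 0.5 and balanced baselines (so zero covariance). The Fieller 95% interval for 0.58 is 0.27 to 1.00 unadjusted. With both variances multiplied by 0.75 it is 0.31 to 0.93.

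**3. Size of chance imbalance.** The SD of the difference in mean baseline, in units of s0, is √(1/n1 + 1/n2):

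| Contrast | SD of difference | P(imbalance > 0.5 s0) |
|---|---|---|
| 14 vs 16 | 0.366 | 17% |
| 14 vs 14 | 0.378 | 19% |
| 14 vs 20 | 0.348 | 15% |

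**4. Carry-over into the ratio.** The part left in the change score is (1 − b) × imbalance. With s0 = 0.8 and b = 0.5, a one-standard-error imbalance for 14 vs 16 is 0.8 × 0.366 = 0.29 log10, and (1 − 0.5) × 0.29 = 0.146 of it stays in the contrast. Splitting this about the overall mean baseline (16/30 to the test arm, 14/30 to RHEZ) gives (0.84 + 0.078)/(1.44 − 0.068) = 0.67. At b = 0.3 the ratio is 0.71, at b = 0.7 it is 0.63, and at b = 1 it stays at 0.58.

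**The case against.** A reader might infer four stronger things. The documents do not support them.

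- **That the plan ignores baseline load.** It does not. EBA is baseline minus Day 14. What is missing is adjustment of that change for baseline.
- **That every EBA ratio interval is too wide.** The table above shows settings with no gain, or a loss of about 2%. Nothing in the documents says which setting applies. Using the mean of two baseline collections, and of duplicate plates where available, also reduces regression to the mean.
- **That chance imbalance makes the intervals invalid.** Between concurrently randomised arms it is already in the unadjusted SE. At equal SDs of 0.8 and r = 0.5 the SD of the change is also 0.8, so the contrast SE is 0.8 × 0.366 = 0.29. The 0.146 shift is half of that SE, not an error on top of it. This defence does not cover systematic differences between cohorts or stages.
- **That no baseline adjustment is planned anywhere.** The mixed model's covariate list is incomplete in the public copy, and the text of SAP 8.3 (Exploratory Analyses) and of Appendix 6 (Technical Details) is not visible. Adjustment there can be neither confirmed nor excluded.

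It can also be said that the trial is not powered for comparisons and that baseline CFU will be tabulated by arm. Both are true. However, intervals for ratios are planned, and a table shows an imbalance without correcting the ratio for it. The mixed model is a separate estimate and leaves the two-point ratio as it is.

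**Conclusion.** The concern holds in a limited form, for the two-point method only. Its ratio rests on unadjusted means of a change score, so baseline differences pass into it in proportion to 1 minus the slope of Day 14 on baseline. In the illustration above, a one-standard-error imbalance moves 0.58 to between 0.63 and 0.71 for slopes of 0.7 down to 0.3. The interval for the EBA difference could be about 6 to 18% narrower if the SDs are equal and the correlation is 0.3 to 0.7; otherwise the gain may be nil or slightly negative. These sizes rest on assumed SDs and correlations. The imbalance argument does not depend on a gain in precision, and it is strongest for the non-concurrent contrasts. The change is worth making because baseline is already collected and the cost is small.

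**What to change.** Estimate the two-point EBA by ANCOVA of the Day 14 change in log10 CFU/mL on treatment and baseline log10 CFU/mL, allowing arm-specific residual variances as the present arm-wise SEs do. One model per stage does not fit the planned comparisons, so specify a model for each set:

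- Stage 1 arms with pooled RHEZ;
- the three Stage 2 combination arms (SAP 8.2 limits that analysis to them);
- Stage 2 arms with pooled RHEZ;
- the cross-stage comparisons with 30 mg alone (Protocol 7.4.2, comparisons 3 and 4).

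Take LS-means at the overall mean baseline of the set, state that reference value because the ratio depends on it, and pass the LS-means with their variances and covariance to Fieller's method. The covariance is generally no longer zero. Keep the unadjusted summary alongside. Do the same for LAM and TTD with their own baselines. State also whether the mixed model adjusts the slope for baseline.

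Cost: a few lines of SAP text and code, one degree of freedom, and a common-slope assumption that the 5 CFU/mL floor may strain. There may be no gain in precision. The adjustment does not remove other cohort or stage period effects.
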